## Implementation Notes:

For the Groups 1 and 3A tables, the time points should be Day 1 (Pre-Vaccination), Day 29 Post Vaccination 1, Day 57 Post Vaccination 1 (29 Days Post Vaccination 2).

For the Groups 3B and 4 tables, the time points should be Day 1 (Pre-Vaccination), Day 29 Post Vaccination 1, Day 85 Post Vaccination 1, Day 99 Post Vaccination 1 (15 Days Post Vaccination 2).

For the Groups 5 and 6 tables, the time points should be: Day 1 (Pre-Vaccination), Day 15 Post Vaccination.

For the Groups 9, 10, and 11 tables, the time points should be: Day 1 (Pre-Vaccination), Day 15 Post Vaccination.

For the Groups 10A, 10B, 11A, and 11B tables, the time points should be: Day 1 (Pre-Vaccination), Day 15 Post Vaccination.

For the Groups 13, 14, and 15 tables, the time points should be: Day 1 (Pre-Vaccination), Day 15 Post Vaccination

Tables with similar format:

**Table 203: Summary of T Cells Expressing Cytokines as measured by the ICS Assay by Time Point and Vaccination Arm - COVID-19 Vaccination Naïve, 18-60 years of age, Groups 1 and 3A, Per Protocol Population**

**Table 204: Summary of T Cells Expressing Cytokines as measured by the ICS Assay by Time Point and Vaccination Arm - COVID-19 Vaccination Naïve, 18-60 years of age, Groups 3B and 4, mITT Population**

**Table 205: Summary of T Cells Expressing Cytokines as measured by the ICS Assay by Time Point and Vaccination Arm - COVID-19 Vaccination Naïve, 18-60 years of age, Groups 3B and 4, Per Protocol Population**

**Table 206: Summary of T Cells Expressing Cytokines as measured by the ICS Assay by Time Point and Vaccination Arm - COVID-19 mRNA Vaccinated, 18-60 years of age, SAM-S-TCE Boosts, mITT Population**

**Table 207: Summary of T Cells Expressing Cytokines as measured by the ICS Assay by Time Point and Vaccination Arm - COVID-19 mRNA Vaccinated, 18-60 years of age, SAM-S-TCE Boosts, Per Protocol Population**

**Table 208: Summary of T Cells Expressing Cytokines as measured by the ICS Assay by Time Point and Vaccination Arm - COVID-19 mRNA Vaccinated, >60 years of age, SAM-S-TCE Boosts, mITT Population**

**Table 209: Summary of T Cells Expressing Cytokines as measured by the ICS Assay by Time Point and Vaccination Arm - COVID-19 mRNA Vaccinated, >60 years of age, SAM-S-TCE Boosts, Per Protocol Population**

**Table 210: Summary of T Cells Expressing Cytokines as measured by the ICS Assay by Time Point and Vaccination Arm - COVID-19 mRNA Vaccinated, >60 years of age, ChAd-S-TCE Boosts, mITT Population**

**Table 211: Summary of T Cells Expressing Cytokines as measured by the ICS Assay by Time Point and Vaccination Arm - COVID-19 mRNA Vaccinated, >60 years of age, ChAd-S-TCE Boosts, Per Protocol Population**

## 14.3 Safety Data

### 14.3.1 Displays of Adverse Events

**Table 212: Overall Summary of Adverse Events by Vaccination Arm – COVID-19 Vaccination Naïve, 18-60 years of age, Groups 1 and 3A**

Participants a with		Group 1: $5 \times 10^{10}$ vp ChAd-S/30 µg SAM-S (N=X)		Group 3A: 30 µg SAM-S/30 µg SAM-S (N=X)		All Participants (N=X)	
Category 1	Category 2	n	%	n	%	n	%
At least one local solicited adverse event	NA						
At least one systemic solicited adverse event	NA						
At least one unsolicited adverse event	NA						
At least one related unsolicited adverse event	Any Grade						
	Mild (Grade 1)						
	Moderate (Grade 2)						
	Severe (Grade 3)						
At least one severe (Grade 3) unsolicited adverse event	Any relationship						
Related	Related						
Unrelated	Unrelated						
At least one serious adverse event b	Any relationship						
	Related						
At least one adverse event leading to early termination c	NA						
At least one adverse event leading to treatment discontinuation	NA						
Any laboratory Adverse Event	NA						

Participants a with		Group 1: $5 \times 10^{10}$ vp ChAd-S/30 µg SAM-S (N=X)		Group 3A: 30 µg SAM-S/30 µg SAM-S (N=X)		All Participants (N=X)	
Category 1	Category 2	n	%	n	%	n	%
Any Vital Signs Adverse Event	NA						
At least one medically attended adverse event	NA						
At least one new onset chronic medical condition	NA						

N = Number of participants in the Safety Population  
aParticipants are counted once for each category regardless of the number of events.  
bA listing of Serious Adverse Events is included in [Table 307](#).  
cAs reported on the Adverse Event eCRF.

## Implementation Notes:

For the Groups 5-15 tables, do not include the “At least one adverse event leading to treatment discontinuation” row, as those groups have only one study vaccination.]

Tables with similar format:

**Table 213: Overall Summary of Adverse Events by Vaccination Arm – COVID-19 Vaccination Naïve, 18-60 years of age, Groups 3B and 4**

**Table 214: Overall Summary of Adverse Events by Vaccination Arm – COVID-19 mRNA Vaccinated, 18-60 years of age, SAM-S-TCE Boosts**

**Table 215: Overall Summary of Adverse Events by Vaccination Arm – COVID-19 mRNA Vaccinated, >60 years of age, SAM-S-TCE Boosts**

**Table 216: Overall Summary of Adverse Events by Vaccination Arm – COVID-19 mRNA Vaccinated, >60 years of age, ChAd-S-TCE Boosts**

**Table 217: Adverse Events Occurring in 5% of Participants in Any Vaccination Arm by MedDRA System Organ Class and Preferred Term, and Vaccination Arm – COVID-19 Vaccination Naïve, 18-60 years of age, Groups 1 and 3A**

Preferred Term	MedDRA System Organ Class	Group 1: 5 x 10  vp ChAd-S/30 µg SAM-S (N=X)			Group 3A: 30 µg SAM-S/30 µg SAM-S (N=X)			All Participants (N=X)		
		n	%	Events	n	%	Events	n	%	Events
Serious Adverse Events										
All	All	x	x	x	x	x	x	x	x	x
PT1	SOC1	x	x	x	x	x	x	x	x	x
Etc.	Etc.									
Non-serious Adverse Events										
All	All	x	x	x	x	x	x	x	x	x
PT1	SOC1	x	x	x	x	x	x	x	x	x
Etc.	Etc.									
Solicited Adverse Events										
All	All	x	x	x	x	x	x	x	x	x
PT1	SOC1	x	x	x	x	x	x	x	x	x
Etc.	Etc.									
Any Adverse Event										
All	All	x	x	x	x	x	x	x	x	x

N = number of participants in the Safety Population (number of participants at risk).

n = number of participants reporting event.

Events = total frequency of events reported.

Solicited events ongoing past Day 8 are included as unsolicited events.

Tables with Similar Format:

**Table 218:** Adverse Events Occurring in 5% of Participants in Any Vaccination Arm by MedDRA System Organ Class and Preferred Term, and Vaccination Arm – COVID-19 Vaccination Naïve, 18-60 years of age, Groups 3B and 4

**Table 219:** Adverse Events Occurring in 5% of Participants in Any Vaccination Arm by MedDRA System Organ Class and Preferred Term, and Vaccination Arm – COVID-19 mRNA Vaccinated, 18-60 years of age, SAM-S-TCE Boosts

**Table 220:** Adverse Events Occurring in 5% of Participants in Any Vaccination Arm by MedDRA System Organ Class and Preferred Term, and Vaccination Arm – COVID-19 mRNA Vaccinated, >60 years of age, SAM-S-TCE Boosts

**Table 221:** Adverse Events Occurring in 5% of Participants in Any Vaccination Arm by MedDRA System Organ Class and Preferred Term, and Vaccination Arm – COVID-19 mRNA Vaccinated, >60 years of age, ChAd-S-TCE Boosts

**14.3.1.1      Solicited Adverse Events****Table 222: Number and Percentage of Participants Experiencing Solicited Events by Symptom, Maximum Severity, Dose, and Vaccination Arm - COVID-19 Vaccination Naïve, 18-60 years of age, Groups 1 and 3A – Dose 1**

		Group 1: 5 x 10  vp ChAd-S/30 µg SAM-S (N=X)		Group 3A: 30 µg SAM-S/30 µg SAM-S (N=X)		All Participants (N=X)	
Symptom	Severity	n	%	n	%	n	%
Any Symptom	None						
	Mild						
	Moderate						
	Severe						
Any Systemic Symptom	None						
	Mild						
	Moderate						
	Severe						
Arthralgia	None						
	Mild						
	Moderate						
	Severe						
Diarrhea	None						
	Mild						
	Moderate						
	Severe						
Fatigue	None						
	Mild						
	Moderate						
	Severe						

		Group 1: $5 \times 10^{10}$ vp ChAd-S/30 µg SAM-S (N=X)		Group 3A: 30 µg SAM-S/30 µg SAM-S (N=X)		All Participants (N=X)	
Symptom	Severity	n	%	n	%	n	%
Fever a	None						
	Mild						
	Moderate						
	Severe						
Feverishness	None						
	Mild						
	Moderate						
	Severe						
Headache	None						
	Mild						
	Moderate						
	Severe						
Malaise	None						
	Mild						
	Moderate						
	Severe						
Myalgia	None						
	Mild						
	Moderate						
	Severe						
Nausea	None						
	Mild						
	Moderate						
	Severe						

		Group 1: $5 \times 10^{10}$ vp ChAd-S/30 µg SAM-S (N=X)		Group 3A: 30 µg SAM-S/30 µg SAM-S (N=X)		All Participants (N=X)	
Symptom	Severity	n	%	n	%	n	%
Any Local Symptom	None						
	Mild						
	Moderate						
	Severe						
Erythema/Redness	None						
	Mild						
	Moderate						
	Severe						
Erythema/Redness Measurement (mm)	None						
	Mild						
	Moderate						
	Severe						
Induration/Swelling	None						
	Mild						
	Moderate						
	Severe						
Induration/Swelling Measurement (mm)	None						
	Mild						
	Moderate						
	Severe						
Pain	None						
	Mild						
	Moderate						
	Severe						

Severity is the maximum severity reported over all solicited symptoms post dosing for each participant.  
N=All participants receiving vaccination with any solicited event data recorded in the database.

Tables with similar format:

**Table 223:** Number and Percentage of Participants Experiencing Solicited Events by Symptom, Maximum Severity, Dose, and Vaccination Arm - COVID-19 Vaccination Naïve, 18-60 years of age, Groups 1 and 3A – Dose 2

**Table 224:** Number and Percentage of Participants Experiencing Solicited Events by Symptom, Maximum Severity, Dose, and Vaccination Arm - COVID-19 Vaccination Naïve, 18-60 years of age, Groups 1 and 3A – Any Dose

**Table 225:** Number and Percentage of Participants Experiencing Solicited Events by Symptom, Maximum Severity, Dose, and Vaccination Arm - COVID-19 Vaccination Naïve, 18-60 years of age, Groups 3B and 4 – Dose 1

**Table 226:** Number and Percentage of Participants Experiencing Solicited Events by Symptom, Maximum Severity, Dose, and Vaccination Arm - COVID-19 Vaccination Naïve, 18-60 years of age, Groups 3B and 4 – Dose 2

**Table 227:** Number and Percentage of Participants Experiencing Solicited Events by Symptom, Maximum Severity, Dose, and Vaccination Arm - COVID-19 Vaccination Naïve, 18-60 years of age, Groups 3B and 4 – Any Dose

**Table 228:** Number and Percentage of Participants Experiencing Solicited Events by Symptom, Maximum Severity, Dose, and Vaccination Arm - COVID-19 mRNA Vaccinated, 18-60 years of age, SAM-S-TCE

**Table 229:** Number and Percentage of Participants Experiencing Solicited Events by Symptom, Maximum Severity, Dose, and Vaccination Arm - COVID-19 mRNA Vaccinated, >60 years of age, SAM-S-TCE Boosts

**Table 230:** Number and Percentage of Participants Experiencing Solicited Events by Symptom, Maximum Severity, Dose, and Vaccination Arm - COVID-19 mRNA Vaccinated, >60 years of age, ChAd-S-TCE Boosts

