## 9. SAFETY EVALUATION

Summaries and analyses of safety data will be presented for the safety analysis population.

Solicited non serious AEs will be collected from the time of each vaccination until 7 days after. Solicited AEs will be summarized by severity for each day post each vaccination and as the maximum severity over all 8 days. Additionally, solicited AEs will be analyzed using standard techniques, such as 95% CIs (using the Clopper-Pearson method), to summarize the proportion of participants reporting each symptom, any local (vaccination site) symptom, and any systemic symptom.

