### 9.3.1. Solicited Events and Symptoms

Systemic solicited AEs were collected pre-vaccination, and systemic and local solicited AEs were collected 30 minutes post-vaccination and then daily for 7 days after each vaccination. Solicited local events include erythema (redness), induration (hardness)/edema (swelling), pain, and tenderness. Solicited systemic events include fever, chills (feverishness), fatigue (tiredness), malaise (general unwell feeling), myalgia (body aches/muscular pain exclusive of the injection site), arthralgia (joint pain exclusive for the injection site), headache, nausea, and diarrhea. Solicited events were graded on a scale of none (absent), mild, moderate, and severe. Measurement values for erythema and induration (hardness)/edema (swelling) were collected and graded based on the FDA Toxicity Grading Scale for Healthy Adult and Adolescent Volunteers Enrolled in Preventative Vaccine Clinical Trials [[4](#)].

Solicited AEs are summarized by severity pre-vaccination (systemic solicited AEs only), post-vaccination, and each day post-study vaccination (Days 1-8). Solicited AEs are also summarized by the maximum severity over all post-vaccination measurements. The proportions of participants reporting each symptom, any local symptom, any systemic symptom, and any symptom are summarized by vaccination arm separately for each dose and both doses combined (where applicable). For each event the denominator is the number of participants with non-missing data for the event.

The following summaries for solicited adverse events are presented by maximum severity, vaccination (each dose separately and both doses combined, where applicable), and vaccination arm:

- Number and percentage of participants experiencing solicited events by symptom and maximum severity, for any symptom, local symptoms, and systemic symptoms (beginning with [Table 222](#) and ending with [Table 230](#))
- Number and percentage of participants experiencing any solicited event, any systemic event, any local symptom, and each symptom, by day and severity, for each vaccination (starting with [Table 231](#) and ending with [Table 250](#))

- Duration of solicited symptoms summarized by mean, standard deviation, median, minimum, and maximum by symptom, dose, and vaccination arm ([Table 251](#), [Table 252](#), [Table 253](#), [Table 254](#), and [Table 255](#))

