Symptom	Severity	n	%	n	%	n	%	n	%	n	%	n	%	n	%	n	%	n	%	n	%		
Nausea	None																						
	Mild																						
	Moderate																						
	Severe																						
	Not Reported																						
Any Local Symptom	None																						
	Mild																						
	Moderate																						
	Severe																						
	Not Reported																						
Erythema	None																						
	Mild																						
	Moderate																						
	Severe																						
	Not Reported																						
Erythema Measurement (mm)	None																						
	Mild																						
	Moderate																						
	Severe																						
	Not Reported																						
Edema/Induration	None																						
	Mild																						
	Moderate																						
	Severe																						
	Not Reported																						

		Pre-Dose ( N=X )		Post-Dose (N=X)		Day 1 (N=X)		Day 2 (N=X)		Day 3 (N=X)		Day 4 (N=X)		Day 5 (N=X)		Day 6 (N=X)		Day 7 (N=X)		Day 8+  (N=X)		Any Post-Dose 	
Symptom	Severity	n	%	n	%	n	%	n	%	n	%	n	%	n	%	n	%	n	%	n	%		
Edema/Induration Measurement (mm)	None																						
	Mild																						
	Moderate																						
	Severe																						
	Not Reported																						
Pain	None																						
	Mild																						
	Moderate																						
	Severe																						
	Not Reported																						
Tenderness	None																						
	Mild																						
	Moderate																						
	Severe																						
	Not Reported																						

Severity is the maximum severity reported post dosing for each participant for each day.

 Day 8+ includes the maximum severity of each symptom reported on or after Day 8 (includes ongoing symptoms)

Indicates how many participants had “None”, “Mild”, “Moderate”, “Severe”, or “Not Reported” as their maximum severity for any day. A participant may be counted in more than one of these categories.

Tables with similar format:

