**Table 323: Laboratory Summary Statistics by Parameter, Time Point, and Vaccination Arm – Creatine Kinase**

**Table 324: Laboratory Summary Statistics by Parameter, Time Point, and Vaccination Arm – Creatinine**

**14.3.5.2 Hematology Results****Table 325: Laboratory Results by Parameter, Maximum Severity, Time Point, and Vaccination Arm – Any Hematology Parameter**

Time Point	Vaccination Arm	N	None		Mild/ Grade 1 (Low)		Mild/ Grade 1 (High)		Moderate/ Grade 2 (Low)		Moderate/ Grade 2 (High)		Severe/ Grade 3 (Low)		Severe/ Grade 3 (High)		Missing	
			n	%	n	%	n	%	n	%	n	%	n	%	n	%	n	%
Baseline	Group 1: $5 \times 10^{10}$ vp ChAd/ 30 µg SAM-S	x	x	x	x	x	x	x	x	x	x	x	x	x	x	x	x	
	Group 3A: 30 µg SAM-S/ 30 µg SAM-S																	
	Group 3B: 30 µg SAM-S/ 3 µg SAM-S																	
	Group 4: 10 µg SAM-S-TCE/ 3 µg SAM-S-TCE																	
	Group 5: 3 µg SAM-S-TCE																	
	Group 6: 6 µg SAM-S-TCE																	
	Group 9: 3 µg SAM-S-TCE																	
	Group 10: 6 µg SAM-S-TCE																	
	Group 11: 10 µg SAM-S-TCE																	
	Group 13: $5 \times 10^{10}$ vp ChAd-S-TCE																	
	Group 14: $1 \times 10^{11}$ vp ChAd-S-TCE																	
	Group 15: $5 \times 10^{11}$ vp ChAd-S-TCE																	
All Participants																		

Time Point	Vaccination Arm	N	None		Mild/ Grade 1 (Low)		Mild/ Grade 1 (High)		Moderate/ Grade 2 (Low)		Moderate/ Grade 2 (High)		Severe/ Grade 3 (Low)		Severe/ Grade 3 (High)		Missing	
			n	%	n	%	n	%	n	%	n	%	n	%	n	%	n	%
Day 8	...																	
Day 29 (pre-dose 2 for Groups 1 and 3A)	...																	
Day 36 (8 days post-dose 2 for Groups 3A and 4)	...																	
Day 85 (pre-dose 2 for Groups 3B and 4)	...																	
Day 92 (8 days post-dose 2 for Groups 3B and 4)	...																	
Max Severity Post Baseline	...																	

Note: The “Maximum Post Baseline” rows indicate the maximum severity experienced by each vaccination group at any time point post baseline, including unscheduled assessments.  
N = Number of participants in the Safety Analysis Population

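### The Table 222 footnote (reused for Tables 223-230) takes maximum severity across all solicited symptoms, contradicting the per-symptom maximum over time in SAP Sections 9 and 9.3.1

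*SAP*

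**What the plan says.** The shell is in SAP Appendix 1, section 14.3.1.1. Table 222 is titled "Number and Percentage of Participants Experiencing Solicited Events by Symptom, Maximum Severity, Dose, and Vaccination Arm", for Groups 1 and 3A, Dose 1. It has None, Mild, Moderate and Severe rows for each symptom and for Any Symptom, Any Systemic Symptom and Any Local Symptom. Its footnote gives the only definition of severity: "Severity is the maximum severity reported over all solicited symptoms post dosing for each participant". Tables 223-230 are listed as having a similar format, so the definition carries over to them.

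The analysis text gives a different rule:

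- Section 9: "Solicited AEs will be summarized by severity for each day post each vaccination and as the maximum severity over all 8 days".
- Section 9.3.1: "Solicited AEs are also summarized by the maximum severity over all post-vaccination measurements".
- Section 9.3.1, describing Tables 222-230: "Number and percentage of participants experiencing solicited events by symptom and maximum severity, for any symptom, local symptoms, and systemic symptoms".
- Section 9.3.1, on denominators: "For each event the denominator is the number of participants with non-missing data for the event".

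The by-day shell, Table 231, does not refer to all solicited symptoms: "Severity is the maximum severity reported post dosing for each participant for each day".

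**The concern.** The footnote and the analysis text take the maximum over different things. The text takes it over time, within the symptom being tabulated. The footnote takes it over symptoms, within the participant. In a table with one block per symptom, the footnote's rule would place the grade of one symptom in the row of another.

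Safety and tolerability are the primary objective, and Section 9.3.1 assigns the worst grade by symptom and dose to Tables 222-230. Table 231 onward does not clearly supply that statistic: the note to its any-post-dose column allows a participant to be counted in more than one severity category. Planned arms are small, from 3 participants in Groups 3A and 4 up to 12, so one misplaced grade visibly changes a percentage.

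**Working it through.** The SAP states no figure that depends on this footnote, so there is nothing to reproduce. The check has three parts.

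**1. The rules compared**

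| Place in SAP | Maximum taken over | Unit tabulated |
|---|---|---|
| Section 9 | the 8 days | solicited AE |
| Section 9.3.1 | post-vaccination measurements | symptom, plus any, local and systemic |
| Table 222 title and rows | not stated | symptom, plus three Any blocks |
| Table 222 footnote | all solicited symptoms | participant |

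Only the Any Symptom block satisfies both rules. Any Systemic and Any Local need a maximum over their own class. Each symptom block needs a maximum over that symptom alone.

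**2. A small invented example**

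Four participants (the size of Group 1) and three symptoms, each graded at its worst over the post-dose days:

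- A: pain severe, headache mild, fever none
- B: pain mild, headache none, fever none
- C: pain moderate, headache moderate, fever mild
- D: none for all three

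Counts are None / Mild / Moderate / Severe.

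| Block | Section 9.3.1 rule | Footnote, literal |
|---|---|---|
| Pain | 1/1/1/1 | 1/1/1/1 |
| Headache | 2/1/1/0 | 1/1/1/1 |
| Fever | 3/1/0/0 | 1/1/1/1 |
| Any Symptom | 1/1/1/1 | 1/1/1/1 |

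The literal rule makes every block equal to Any Symptom. It adds one severe headache and one severe fever that did not occur. It leaves Any Symptom unchanged.

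If a programmer applied the footnote only to participants who report the symptom, the Mild/Moderate/Severe counts would go from 1/1/0 to 0/1/1 for headache and from 1/0/0 to 0/1/0 for fever. The blocks would then differ from one another, so the error would be harder to see.

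**3. How large the effect could be**

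Section 9.3.1 lists 13 solicited symptoms, 9 systemic and 4 local. The severe rates p below are assumptions; the SAP gives none. If severe events are independent across symptoms, a literal symptom row shows 1 − (1 − p)^13.

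| Assumed p | Literal symptom row | Ratio to p |
|---|---|---|
| 1% | 12.2% | 12.2 |
| 2% | 23.1% | 11.5 |
| 5% | 48.7% | 9.7 |
| 10% | 74.6% | 7.5 |

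If severe events always fall in the same participants, the ratio is 1 and the severe counts do not change.

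The composite blocks move less, even under independence:

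- Any Systemic, correct value 1 − (1 − p)^9: 16.6% at p = 2% against 23.1% literal (1.4-fold); 37.0% at p = 5% against 48.7% (1.3-fold).
- Any Local, correct value 1 − (1 − p)^4: 7.8% against 23.1% (3.0-fold); 18.5% against 48.7% (2.6-fold).
- Any Symptom: no change.

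**The case against.** The strongest reply is that the plan already fixes the rule. The table title, the row structure, Sections 9 and 9.3.1 and the event-specific denominator all point to a maximum within symptom over time. A fully literal table would have identical blocks, down to the None counts, and a competent programmer would notice. Symptom-level severity also remains visible in Table 231 onward, in Figures 579-653 and in Listings 9 and 10. No formal hypothesis testing is planned, and the collected data are unaffected.

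Most of this stands. A reader might infer that the plan overstates severe rates, or that the symptom profile by dose could not be read. The documents support neither. Overstatement occurs only if the footnote is followed against the analysis text, and the other displays would still show severity by symptom. Nor can a fixed inflation factor be claimed: the rates are assumed, clustering of severe events can remove the effect, and the composite blocks move far less than the single-symptom rows.

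What the reply does not remove is the contradiction. The footnote is set as a table note rather than as an implementation note, so it would be expected to print. It would then misdescribe tables that had been programmed correctly.

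**Conclusion.** The point holds as a contradiction between a shell footnote and the analysis text. The footnote's definition is right for one block of the table and wrong for every other. The intended analysis is clear from Sections 9 and 9.3.1, so this is a wording error rather than a poor choice of analysis. It is still worth correcting because it is the only severity definition in the shells for worst-grade reactogenicity, which belongs to the primary objective.

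The consequence depends on how the tables are programmed. Under the Section 9.3.1 rule, the numbers are right and the footnote is wrong. Under the literal rule, a participant with one severe symptom counts as severe in every row. The severe percentage in a single-symptom row could then run from unchanged to about 12 times the true value, assuming 13 symptoms with a common severe rate of 1% to 10% and anything from complete clustering to independence. The Any Symptom block is correct either way.

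The Table 325 note is a separate and smaller slip. It says the "rows indicate the maximum severity experienced by each vaccination group at any time point post baseline, including unscheduled assessments", while the matching chemistry shell, Table 312, takes the maximum by participant. A single grade per group cannot fill a table of counts and percentages, so the intent is plain. It adds no weight to the main point.

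**What to change.** Replace the Table 222 footnote, and carry the new text to Tables 223-230: *For each symptom, severity is the participant's maximum severity of that symptom over all post-dose assessments for the dose(s) shown; for Any, Any Systemic and Any Local Symptom it is the maximum over the symptoms in that class.*

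As a minor consistency correction, change the unit in the Table 325 note from vaccination group to participant, to match Table 312.

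Both are wording changes to the SAP shells. They need no new data and no change to the analysis described in Sections 9 and 9.3.1. If the tables have already been programmed, check that the code takes the maximum within symptom.
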